## Abstract

Title	Psilocybin-Assisted Group Therapy for Demoralization in Long-term AIDS Survivors
Patient population	Gay-identified HIV-positive men $\geq 50$ years old who were diagnosed with HIV prior to 1996.
Rationale for Study	
Long-term AIDS Survivors (LTAS) are people living with HIV (PLH) who were diagnosed prior to the advent of combined antiretroviral therapy (ART) and, compared to their HIV seronegative peers, suffer higher rates of depression, anxiety, trauma exposure, substance use and risky sexual behaviors [1-6]. Prior to ART, people living with HIV were “end-of-life patients,” then with advent of ART they became “chronically ill,” and now many of them are re-approaching end-of-life status as their bodies age at an accelerated rate due to HIV infection, HIV therapies, HIV-associated non-AIDS conditions, or all of the above [7]. By 2014, 9,202 HIV-positive individuals living in San Francisco were older than 50 years old (58% of the city’s HIV-positive population) [8]. Like “cancer survivors,” AIDS survivors experience increased rates of psychological distress even long after their disease is controlled [9, 10]. LTAS are an emerging population whose mental health needs are under recognized and undertreated.
 
Existential distress is a form of psychological suffering precipitated by the acute awareness of one’s mortality [11]. Demoralization is one type of existential distress [12], and it is characterized by a sense of hopelessness, helplessness and a loss of meaning in life [13]. Demoralization is a well-characterized clinical syndrome that captures the form of psychological distress suffered by many LTAS [1, 14]. Demoralization is also a clinical construct well-suited for investigation as a hypothesized therapeutic benefit of psilocybin-assisted psychotherapy in a population with chronic existential distress, like LTAS. Because it is experienced as a loss of meaning, demoralization should theoretically be treatable with interventions that enhance meaning-making [15]. An investigational pharmacotherapy that is thought to potentially enhance meaning-making is psilocybin [16, 17]. Recent trials of individual psilocybin-assisted psychotherapy for anxiety and depression in cancer patients have shown this intervention to be safe [18-20], and have found significant improvements in anxiety and depression lasting months after a single treatment [19, 20]. Such impressive results are thought to be mediated by two mechanisms: 1) Having a complete “mystical-type” experience under the influence of psilocybin [21], and 2) Subsequent enhanced social support in the weeks following the mystical experience [22]. It remains unknown how these impressive results may translate into other palliative care populations.
 
Since the beginning of the HIV/AIDS epidemic, many psychotherapies for people living with HIV have been preferentially delivered as groups because of enhanced cost-effectiveness and the group format’s unique clinical benefits with respect to the enhancement of social support in a population suffering high rates of isolation and loneliness [23]. This study will use the same standard psilocybin administration safety guidelines


Rationale for Study (continued)	
as prior trials [24], but the psychotherapy sessions will employ a modified form of Supportive-Expressive Group Therapy (SEGT) [25]. SEGT is a widely used, manualized, evidence-based group intervention for existential distress in patients with life-threatening disease [26]. The current study will be the first modern study of psilocybin-assisted group psychotherapy.
 
In the current study, the group psychotherapy format functions as a standardized context in which patients' experiences of social support can be objectively observed pre- and post-psilocybin. This is helpful because while prior trials of psilocybin-assisted psychotherapy evaluated clinical outcomes, they did not make use of validated measures of psychotherapeutic process. By administering psilocybin as an adjunct to SEGT, we will be able to explore quantitatively and qualitatively not only the intrapersonal, but also the interpersonal, therapeutic mechanisms catalyzed by psilocybin in LTAS suffering from demoralization.

Primary Objective	To demonstrate the safety and feasibility of Psilocybin-Assisted Supportive-Expressive Group Therapy (PA-SEGT) for demoralization in LTAS.
Exploratory Objectives	
To explore the preliminary efficacy of PA-SEGT for improving demoralization, complicated grief, depression, anxiety, quality of life, functional social support, post-traumatic growth, openness to experience, mindfulness, social connection, nature relatedness and ART medication adherence in LTAS.
 
To explore quantitatively and qualitatively the mechanisms through which PA-SEGT addresses existential distress in LTAS.

Study Design	Open-label mixed-methods pilot study of individual oral psilocybin drug sessions (with escalating dose) combined with an evidence-based, manualized brief group psychotherapy.
Number of patients	36 (maximum, with a minimum of 8)
Duration of Therapy	8 weeks after the initiation of the intervention.
Duration of Follow up	3 months after completion of the intervention.
Duration of study	2 years from the time the study opens to accrual.
Study Therapy	Psilocybin (4-phosphoryloxy-N,N-dimethyltryptamine) will be administered once at a moderate-to-high dose of 0.3mg/kg (or 0.36mg/kg) po during an individual medication visit to be held after 4 group therapy visits have been completed. Patients will undergo a total of 10 group psychotherapy sessions.

Safety Assessments	Adverse events Vital signs  Adverse Event Medication Session Form  Columbia Suicide Severity Rating Scale  Community Observer Rating Form
Feasibility Assessments	Rate of Patient Recruitment Rate of Patient Retention (Sessions Attended and Follow-ups Completed) Client Satisfaction Scale Individual Patient and Important Other/Caregiver Interviews Supportive-Expressive Group Therapy Topic Grid Focus Groups with Patients and Important Others/Caregivers
Primary Outcomes	Demoralization Scale-II Inventory of Complicated Grief
Secondary Outcomes	Antiretroviral Medication Adherence Scale Alcohol Use Disorders Identification Test Center for Epidemiologic Studies Depression Scale—Revised Challenging Experience Questionnaire Clinical Global Impressions Scale Credibility/Expectancy Questionnaire Duke/UNC Functional Social Support Questionnaire—5 Drug Use Disorders Identification Test Experiences in Close Relationships scale—Modified 16 Group Psychotherapy Intervention Rating Scale Group Questionnaire HIV and Abuse Related Shame Inventory Individual Group Member Interpersonal Process Scale International Personality Item Pool—Openness to Experience-20 McGill Quality of Life Questionnaire—Revised-Short Multidimensional Assessment of Interoceptive Awareness—Revised Mystical Experience Questionnaire—30 Nature Relatedness Scale, Short Form Post-traumatic Growth Inventory—Short Form PTSD Checklist-5 Schedule of Attitudes towards Hastened Death Social Connectedness Scale-Revised

	State-Trait Anxiety Inventory Qualitative analysis of therapy sessions, interviews & focus groups
--	--

Unique Aspects of this Study	
This trial will be the first clinical trial of psilocybin-assisted psychotherapy for LTAS. It will also be the first modern trial of psilocybin-assisted group psychotherapy. It will be the first study of psilocybin-assisted psychotherapy for existential distress that will employ an evidence-based psychotherapy in the non-drug therapy sessions. The study will provide the first safety data for the use of this intervention in LTAS. It will not only yield preliminary data on the potential efficacy of this novel intervention, but it will also be the first study to employ both validated quantitative measures and qualitative methods in the analysis of the psychotherapeutic processes germane to psilocybin-assisted psychotherapy. It will also be the first clinical trial of psilocybin-assisted psychotherapy to assess the impact of the intervention on quality of life in partners/caregivers of LTAS. In anticipation of larger, better powered trials, clinical outcomes from this Phase I study will be used to produce the first estimates of effect size of this novel treatment for demoralization in palliative care patients.

------------------------------	--

## Abbreviations

AGPA	American Group Psychotherapy Association
AHP	Alliance Health Project
AIDS	Acquired Immune Deficiency Syndrome
Albumin	Alb
AlkPhos	Alkaline phosphatase
Alt	Alanine aminotransferase
AMAS	Antiretroviral Medication Adherence Scale
AMAS	ART Medication Adherence Scale
ANOVA	Analysis of Variance
ART	Antiretroviral Therapy
Ast	Aspartate aminotransferase
AUDIT	Alcohol Use Disorders Identification Test
BUN	Blood Urine Nitrogen
CBC	Complete Blood Count
ChEQ	Challenging Experience Questionnaire
CrEQ	Credibility/Expectancy Questionnaire
CESD-R	Centers for Epidemiologic Studies Depression Scale—Revised
CHR	Committee on Human Research
CMP	Comprehensive Metabolic Panel
CORF	Community Observer Rating Form
Cr	Creatinine
CSS	Client Satisfaction Scale
C-SSRS	Columbia Suicide Severity Rating Scale
CTC	Concomitant Therapeutics Checklist
DEA	Drug Enforcement Agency
DS-II	Demoralization Scale—II
DSM	Data and Safety Monitor
DUDIT	Drug Use Disorders Identification Test
DUFSS-5	Duke UNC Functional Social Support Questionnaire-5
ECG	Electrocardiogram
ECR-M16	Experiences in Close Relationships scale—Modified 16
ES	Effect Size
FDA	Food and Drug Administration
FT4	Free thyroxine
Gluc	Glucose
GPIRS	Group Psychotherapy Intervention Rating Scale
GQ	Group Questionnaire
HAART	Highly Active Antiretroviral Therapy
HANA	HIV-Associated Non-AIDS
HARSI	HIV and Abuse Related Shame Inventory
Hct	Hematocrit
Hgb	Hemoglobin
HIM	Hill Interaction Matrix
HIPPA	Health Insurance Portability and Accountability Act
HIV	Human Immunodeficiency Virus
ICC	Intraclass Correlation Coefficient
ICF	Informed Consent Form
ICG	Inventory of Complicated Grief
IND	Investigational New Drug
IOS	Inclusion of Other in the Self
IPA	Interpretive Phenomenological Analysis
IPIP-OE-20	International Personality Item Pool—Openness to Experience-20
LPPI	Langley Porter Psychiatric Institute
LSD	Lysergic acid diethylamide-25

[figure not shown]
---

LTAS	Long-term AIDS Survivor
MAIA	Multidimensional Assessment of Interoceptive Awareness
MAOI	Monoamine Oxidase Inhibitors
MEQ-30	Mystical Experience Questionnaire—30
MOCA	Montreal Cognitive Assessment
MQoL-RS	McGill Quality of Life Questionnaire—Revised-Short
NR	Nature Relatedness Scale, Short Form
NEO-PI-R	Revised NEO Personality Inventory
OPLH	Older People Living with HIV
PA-SEGT	Psilocybin-assisted Supportive-Expressive Group Therapy
PCL-5	PTSD Checklist
PEQ-S	Persisting Effects Questionnaire—Spirituality
PLH	People Living with HIV
Plt	Platelet
PPSv2	Palliative Performance Scale version 2
PTG	Post-Traumatic Growth
PTGI-SF	Post-Traumatic Growth Inventory—Short Form
PTSD	Post-Traumatic Stress Disorder
QoLLTI-Fv2	Quality of Life in Life-Threatening Illness—Family Carer Version 2
SAHD	Schedule of Attitudes towards Hastened Death
SCID-5-PD	Structured Clinical Interview for DSM-5 Personality Disorders
SCID-5	Structured Clinical Interview for DSM-5
SCS-R	Social Connectedness Scale-Revised
SEGT	Supportive-Expressive Group Therapy
SEGT-TG	Supportive-Expressive Group Therapy Topic Grid
SNRI	Serotonin-Norepinephrine Reuptake Inhibitors
SSRI	Serotonin Reuptake Inhibitors
STAI	State-Trait Anxiety Inventory
Tbili	Total bilirubin
TCA	Tricyclic Antidepressants
TProt	Total protein
TSH	Thyroid Stimulating Hormone
WBC	White Blood Cell

## 1 Introduction

We propose to conduct a clinical trial of psilocybin-assisted psychotherapy for demoralization in Long-term AIDS Survivors (LTAS). This will be the first trial of psilocybin-assisted psychotherapy specifically for people living with HIV (PLH) and it will be the first modern trial of psilocybin-assisted *group* psychotherapy for any indication. The study will consist of three groups of six gay-identified HIV-seropositive men  $\geq 50$  years of age who were diagnosed with HIV prior to 1996 and who have moderate-to-severe demoralization [27] [13]. Each subject will undergo 8 weeks of a modified form of Supportive-Expressive Group Therapy [25] and one individual psilocybin treatment session [24] half-way through the intervention. Quantitative and qualitative measures of psychotherapeutic process will be used to explore the mechanisms by which this novel therapy seems to work, particularly on the interpersonal level. Quantitative and qualitative measures will assess changes in quality of life of the partners/caregivers of subjects undergoing the intervention. This study will contribute to the available data on the safety, feasibility and efficacy of psilocybin-assisted psychotherapy for existential distress in palliative care patients, and importantly will provide the first of such data on a palliative care population other than cancer patients [28].

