### 6.2 Selection of Measures

Antiretroviral Medication Adherence Scale (AMAS)—A single item 11-point Likert scale (0%-100%) of ART medication adherence percentage over the past week. This scale was invented for this study.

Alcohol Use Disorders Identification Test (AUDIT) – A 10-item screening tool developed by the World Health Organization to assess alcohol consumption, drinking behaviors, and alcohol-related problems.

Center for Epidemiologic Studies Depression Scale-Revised (CES-D-R)—A 20-item validated 5-point Likert scale self-report scale for the detection of depression [155] that has been shown to be sensitive to change in symptoms in palliative care patients. [156].

Client Satisfaction Scale (CSS)—A 4-item 10-point Likert scale (“very dissatisfied” to “very satisfied”) designed for this study assessing satisfaction with the intervention.

Clinical Global Impressions scale (CGI)—A widely-used 3-item clinician-administered assessment developed by the NIMH to assess change in patients in psychopharmacology trials[157].

Challenging Experiences Questionnaire (ChEQ)—A validated 26-item 6-point Likert scale of the extent to which subjects experienced challenging experiences during a psychedelic drug treatment session[158]. The scale has 7 factors: fear, grief, physical distress, insanity, isolation, death and paranoia.

Columbia Suicide Severity Rating Scale (C-SSRS)—A validated 17-item scale that assesses suicidal ideation and behavior ([www.cssrs.columbia.edu](http://www.cssrs.columbia.edu)) according to the Columbia Classification Algorithm for Suicide Assessment (C-CASA), which the FDA Division of Psychiatric Products requires be used in clinical trials it oversees.

Community Observer Rating Form (CORF)—A 13-item 10-point Likert scale developed by Griffiths et al to triangulate behavioral observations of individuals administered psilocybin [17].

Concomitant Therapeutics Checklist (CTC)—A checklist designed for this study to assess the following categories of mental health therapies used over the last week: Prescription medications, non-prescription medications, psychotherapy, mutual aid groups, self-help

techniques, integrative medicine modalities, other.

Credibility/Expectancy Questionnaire (CrEQ)—A 6-item self-report measure of cognitive and affective assessments of a mental health therapy with high internal consistency and good test-retest reliability [159] that we have adapted for psychological distress.

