Palliative Performance Scale version 2 (PPSv2)—A validated clinician-administered tool based on the Karnofsky Performance Scale but adapted for a palliative care population [113, 171].

Persisting Effects Questionnaire—Spirituality (PEQ-S)—An instrument developed by Griffiths et al for subjects who have been administered psilocybin to assess enduring changes in attitudes about life, attitudes about self, mood changes, relationships, behavioral changes, and spirituality [138]. The measure also includes 4 questions about the drug experience itself concerning personal meaningfulness, spiritual significance, how psychologically challenging it was, and personal psychological insights gained. We will only use the Spirituality subscale (59-item, 6 point Likert scale [“none; not at all” to “extreme”]), and the four questions about the psilocybin experience.

Post-traumatic Growth Inventory-Short Form (PTGI-SF)—A validated 10-item 6-point Likert scale meant to assess the following psychological factors in populations that have suffered a traumatic event or major crisis: quality of relationships with others, openness to new possibilities, personal strengths, spiritual change, and appreciation of life [172].

PTSD Checklist (PCL-5): A validated 20-item, 5-point Likert scale (from “Not at All” to “Extremely”) to measure symptom criteria for PTSD from the DSM-5. [Weathers, F.W., Litz, B.T., Keane, T.M., Palmieri, P.A., Marx, B.P., & Schnurr, P.P. (2013). The PTSD Checklist for DSM-5 (PCL-5)]

Quality of Life in Life Threatening Illness Family Caregiver version 2 (QoLLTI-Fv2)—A validated 17-item 11-point Likert scale (0-10) self-report measure that assesses seven domains of quality of life in caregivers for patients with life-threatening illness: state of carer, patient well-being, quality of care, outlook, environment, finances and relationships. This instrument was developed by the same laboratory that developed the McGill Quality of Life scale [173].

Schedule of Attitudes towards Hastened Death (SAHD)—A 20-item True/False self-report measure of the desire for hastened death validated in patients with HIV/AIDS and other palliative care conditions [174].

Social Connectedness Scale-Revised (SCS-R)—A well-validated 8-item 6-point Likert scale (negatively-worded items rated from “strongly agree” to “strongly disagree”) self-report measure which has shown strong construct, convergent and discriminant validity as well as reliability ( $\alpha >$

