### **6.4.5.2 Endpoint (Week 8) Study Measures for Caregivers/Important Others**

Patients' primary caregivers/important others will complete the CORF and CSS.

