### 6.4.6.3 3-Month Patients for Caregivers/Important Others

At 3 Months, primary caregivers/important others will be mailed a packet with the following measures: CORF and CSS. They will be called and encouraged to complete the packet.

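### Section 1 promises quantitative measurement of change in caregivers' quality of life, but the scale selected for it (QoLLTI-Fv2) is given at none of the three caregiver assessments

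*Combined protocol and SAP*

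**What the plan says.** Two narrative statements raise caregiver quality of life. Section 1 says: "Quantitative and qualitative measures will assess changes in quality of life of the partners/caregivers of subjects undergoing the intervention". The abstract, under the study's unique aspects, says the trial will be the first of its kind "to assess the impact of the intervention on quality of life in partners/caregivers of LTAS". The abstract does not say that this will be done quantitatively.

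Section 6.2 describes the QoLLTI-Fv2, a 17-item scale scored 0 to 10, as a "self-report measure that assesses seven domains of quality of life in caregivers for patients with life-threatening illness". The abbreviation list also carries it, as "Quality of Life in Life-Threatening Illness—Family Carer Version 2".

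The caregiver assessments are set out in three places. Section 6.4.3.2 (baseline) lists the CORF alone. Section 6.4.5.2 (Week 8) says "Patients' primary caregivers/important others will complete the CORF and CSS". Section 6.4.6.3 says that at 3 months "primary caregivers/important others will be mailed a packet with the following measures: CORF and CSS". Caregivers are also invited to a brief baseline interview about their relationship with the subject (6.4.3.1), a focus group (6.4.6.1) and a later semi-structured interview (6.4.6.4).

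**The concern.** A quantitative statement about change needs a score before treatment and at least one after it. The plan announces such a statement and describes an instrument for it, but schedules that instrument nowhere. If the schedule is followed, there will be no caregiver quality-of-life numbers to report.

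Timing matters because groups run in sequence (Section 3.1) and baseline measures are taken in the week before the first group session (Section 6.4.3.1). Once a group has started, its caregivers' pre-treatment score is lost. Adding the scale later would give values after treatment with nothing to compare them with.

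**Working it through.** The documents state no figure for this point, so the check is a comparison of sections.

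**Step 1: is the QoLLTI-Fv2 the only candidate?** Yes. It is the only scale in Section 6.2 that measures a caregiver's own quality of life. Where the study will use only part of a scale, 6.2 says so (MQoL-RS, MAIA-R, PEQ-S). It states no such limit for the QoLLTI-Fv2.

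**Step 2: what do caregivers complete?**

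| Time point | Section | Scales listed | Caregiver quality-of-life score |
|---|---|---|---|
| Baseline | 6.4.3.2 | CORF | none |
| Week 8 | 6.4.5.2 | CORF, CSS | none |
| 3 months | 6.4.6.3 | CORF, CSS | none |

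The count is 0 of 3 time points. Neither change from baseline (to Week 8 or to 3 months) can be computed.

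**Step 3: could the CORF or CSS stand in?** No. Section 6.2 says the CORF was developed "to triangulate behavioral observations of individuals administered psilocybin", so its subject is the patient. The CSS has four items on satisfaction with the intervention.

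**Step 4: is the scale picked up elsewhere?** No. The abstract's outcome lists do not name it. The quality-of-life endpoint in Section 2.2.2 concerns the study subject. Section 8.5 plans a median for the CSS and a difference of means for the CORF, and neither 8.5 nor 8.5.1 mentions the QoLLTI-Fv2.

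**Step 5: does the timeline agree?** Its caregiver block has four rows (CORF, CSS, qualitative interview, focus group), none of them the QoLLTI-Fv2. This is only supporting evidence. The table is not a complete record: the IOS, for example, is scheduled in 6.4.3.1 and 6.4.5.1 but has no row. The finding rests on the text of Section 6.4.

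**The case against.** The strongest reply is that the sections that govern conduct agree with one another. The objectives (2.1), hypotheses (1.4), endpoints (2.2) and analyses (8.5) do not contain caregiver quality of life. They use caregivers for acceptability feedback, observation of the patient and understanding of mechanisms, and the CORF, CSS, interviews and focus groups serve those roles. On this reading, the sentence in Section 1 and the entry in 6.2 are leftovers, and nothing operative has been lost. One can add that the scale was built for carers of people with life-threatening illness, whereas Section 1.3 calls this population largely ambulatory.

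Much of this stands. It makes the point minor and makes deletion a legitimate remedy. It does not remove the inconsistency, because the documents nowhere say that the scale was dropped. Absence from the schedule does not show intent either: the PEQ-S is missing from the 3-month packet in 6.4.6.2, yet Section 2.2.1 names it for follow-up and Section 8.5 plans its analysis.

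Three stronger readings are tempting, and the documents do not support them:

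- A reader might infer that a formal trial objective cannot be met. Caregiver quality of life is not among the listed objectives, hypotheses or endpoints.
- A reader might infer that the abstract promises caregiver numbers. It promises only to "assess the impact of the intervention on quality of life in partners/caregivers of LTAS", which qualitative data could satisfy. The quantitative promise rests on the one sentence in Section 1.
- A reader might size the loss from the planned 18 to 36 subjects, counting one caregiver for each. No caregiver number is stated. Caregivers are invited, Section 1.1 says this population has relatively little access to informal caregivers, and Section 6.4.4.2 provides for participants with nobody to take them home.

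The qualitative half of the promise also remains open. The later interview (6.4.6.4) is meant to pick up outcomes that the scales miss. The Appendix C interview guides are not in the text reviewed here, so whether they ask about caregivers' quality of life cannot be settled.

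**Conclusion.** The inconsistency is real and minor. Section 1 promises a quantitative assessment that the schedule cannot deliver: 0 of 3 caregiver time points yield a quality-of-life score, and this holds for any number of caregivers. The aim is secondary and narrative. The primary safety and feasibility analyses and every endpoint listed in Section 2.2 are unaffected.

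The conclusion assumes that Section 6.4 is the complete list of caregiver questionnaires and that the CORF and CSS measure what Section 6.2 says they measure. It does not depend on whether the omission was an oversight or deliberate, because the text needs correcting in either case.

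**What to change.** Choose one of two routes, before the next group's baseline week.

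1. **Keep the measurement.** Add the QoLLTI-Fv2 to 6.4.3.2, 6.4.5.2, 6.4.6.3 and the timeline. Add to 2.2.2 a descriptive exploratory endpoint: change in caregiver score from baseline to Week 8 and to 3 months. Report the number of caregivers contributing at each point. The cost is 17 items at each of three contacts where caregivers already complete forms (17 × 3 = 51 items per caregiver), assumed to take a few minutes per contact, and a modest widening of scope for a pilot. Groups already started would have no baseline.

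2. **Drop the measurement.** If the scale was removed on purpose, delete it from 6.2 and the abbreviation list, take the word quantitative out of the caregiver sentence in Section 1, and limit the abstract's claim to qualitative assessment. This costs only a text amendment, but the trial would then produce no caregiver quality-of-life score. The sponsor should confirm that the caregiver interview and focus-group guides ask about quality of life, so that the remaining claim is supported.
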